The frequencies of these events in study MDX1106-03 (Phase 1 study; N = 306; heavily pre-treated subjects with different tumor types) are summarized in [Table 1.1-1](#). The treatment-related select AEs of Grade 3-4 observed to date are rather uncommon: 6% overall in study MDX1106-03, while their incidence per category varies between 0.3% and 2% (pulmonary AEs). Of note, the 10 mg/kg cohort had numerically greater frequency of such AEs compared with the other dose levels. In the NSCLC subjects treated in the study (n=129) the overall incidence of Grade 3-4 treatment-related select AEs was 5%: 0% for skin and renal AEs, and endocrinopathies; 1% gastrointestinal, hepatic, and infusion reaction AEs; and 2% for pulmonary events.⁷ Most high-grade events of special interest were observed to have resolved while addressed with systemic corticosteroids and/or other immunosuppressive agents. One exception was Grade 4 pneumonitis considered to have led to death of three subjects: two of them were treated at the 1 mg/kg dose level and had NSCLC and CRC, respectively; the third subject had NSCLC and was treated at the 10 mg/kg dose level.

Specific safety algorithms have been designed for the select categories of AEs, and are implemented in a unified manner in all current studies in the nivolumab program (See [Appendix 2](#) for Management Algorithms). These safety algorithms assist the diagnostic, the assessment of relatedness, and the management of the select AEs, also they are continuously evaluated and adjusted as experience accumulates. The current study will focus on improving precision around the frequency of high-grade select AEs, and on obtaining information on their outcome.

Table 1.1-1: Treatment-related Select Adverse Events by Treatment - All CTC Grades Reported in at Least 10 Treated Subjects in MDX1106-03

Preferred Term	0.1 mg/kg n=17		0.3 mg/kg n=18		1 mg/kg n=86		3 mg/kg n=54		10 mg/kg n=131		Total N=306	
	Any Grade	Grade 3-4	Any Grade	Grade 3-4	Any Grade	Grade 3-4	Any Grade	Grade 3-4	Any Grade	Grade 3-4	Any Grade	Grade 3-4
Any Select AE	8 (47)	1 (5.9)	9 (50)	0	42 (49)	3 (4)	23 (43)	2 (4)	58 (44)	13 (10)	140 (46)	19 (6)
Any Endocrinopathies	4 (24)	0	2 (11)	0	9 (11)	0	4 (7)	0	10 (8)	3 (2)	29 (10)	3 (1)
Endocrinopathies Thyroid	3 (18)	0	2 (11)	0	9 (11)	0	4 (7)	0	8 (6)	2 (2)	26 (9)	2 (1)
Blood TSH increased	2 (12)	0	1 (6)	0	2 (2)	0	2 (4)	0	4 (3)	1 (1)	11 (4)	1 (0.3)
Hypothyroidism	1 (6)	0	1 (6)	0	5 (6)	0	1 (2)	0	3 (2)	1 (1)	11 (4)	1 (0.3)

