Also, the large number of subjects enrolled will allow an opportunity to describe, as an exploratory objective, two different treatment durations in terms of safety, efficacy, and patient-reported outcomes (PRO) data. In study MDX1106-03, after 48 weeks of treatment with nivolumab at the 3 mg/kg dose level, 27% of the NSCLC subjects were still on treatment (95% CI: 12.7%, 41.3%). Following on that observation, in the current study, subjects who are still benefiting from the drug after completing 1 year of treatment will be randomized 1:1 in two cohorts. Subjects randomized to Cohort A will continue on treatment until progression, unacceptable toxicity, or withdrawal of informed consent. Subjects randomized to Cohort B will remain on study but will discontinue treatment. Upon disease progression, subjects in Cohort B will be allowed to resume treatment. Subjects randomized to Cohort B who restart treatment will then continue on treatment until progression, unacceptable toxicity, or withdrawal of informed consent.

An additional 500 subjects will be treated under Protocol Amendment 04 (December 2014) to continue collecting safety information and to characterize the outcome of immune-mediated side effects. These additional data will provide a larger data set to inform the risk/benefit profile of the use of nivolumab in lung cancer patients and will help to further clarify the effectiveness of the current treatment algorithms for managing drug- mediated toxicities (See [Appendix 2](#) for Management Algorithms).

1.1.2 *Rationale for Subject Subgroups*

Obtaining additional data on the incidence and outcome of high grade (Grade 3-4 and Grade 5) select events in a similar patient population as that included in the nivolumab registrational NSCLC studies is warranted to further support the assessment of risk/benefit.

Obtaining similar data in patient populations that have been previously excluded from the registrational studies (ie. subjects with PS 2) will provide critical information for the nivolumab clinical development program, and also for medical oncologists when making treatment decisions. Treatment with nivolumab in subjects with PS 2 is planned to allow for signal detection for both safety and efficacy as an exploratory objective (subgroup 4). This data will inform if further investigation of the risk/benefit profile of nivolumab in this subject subset is justified.

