1.4.2 Non-small Cell Lung Cancer (NSCLC) - Background and Treatments

Lung cancer is the leading cause of cancer-related deaths globally. An estimated 221,130 new cases of lung cancer will be diagnosed in 2011.⁴⁴ The majority of subjects (approximately 78%) are diagnosed with advanced or metastatic disease. Progression after first-line therapy occurred in nearly all of these subjects and the 5 year survival rate is only 3.6% in the refractory setting.⁴⁴

There is a particular unmet need among patients who have squamous cell NSCLC (representing up to 25% of all NSCLC) as there are few treatment options after first-line therapy (ie, pemetrexed is not a treatment option.^{2,45} In addition, there are targeted therapeutics that are restricted to the non-squamous population due to adverse events (ie, bevacizumab was associated with fatal hemorrhages in squamous cell subjects).⁴⁶ According to NCCN guidelines, the use of single agent chemotherapy is standard-of-care for patients with recurrent and metastatic NSCLC after failure of platinum-based therapy.⁴⁴ Historical median PFS rates in second-line NSCLC are approximately 2.6 - 3.2 months, and median OS rates approximately 6.7 to 8.3 months (longer in the recent ZODIAC trial, 10+ months).^{30,31,45,47,48} Current therapy in second-line includes docetaxel, erlotinib and pemetrexed (only in non-squamous histologies).^{30,31,45} No agent has shown superiority in OS when compared to docetaxel. Different docetaxel schedules (other than the standard q3 weeks), chemotherapy doublets using docetaxel, and other comparative agents have not shown improvement over docetaxel in this line of therapy.^{49,50,51,52,53}

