8 STATISTICAL CONSIDERATIONS

8.1 Sample Size Determination

In general, for nivolumab monotherapy, the safety profile to date is similar across tumor types, while select treatment related adverse events of high grade (Grade 3-4) are rather uncommon. Their overall incidence was 6% in a previous Phase 1 trial that tested nivolumab at doses between 0.1 mg/kg to 10 mg/kg in 306 subjects with different recurrent or refractory malignancies (MDX-03). The incidence observed for similar AEs 0% in NSCLC subjects (n=129) was 0% for skin and renal AEs, and endocrinopathies; 1% gastro-intestinal, hepatic and infusion reaction AEs, and 2% for pulmonary events.⁷

In order to further characterize the frequency and outcome of such apparently infrequent safety events, the current study will treat with nivolumab approximately 780 subjects who have advanced or metastatic NSCLC and have progressed during or after at least one prior systemic regimen. This sample size will allow for estimating an incidence rate of 0.5% (n=4 subjects with events) with a 95% CI (confidence interval) of (0.14%, 1.31%), or an incidence rate of 2% (n=16 subjects with events) with a 95% CI of (1.18%, 3.31%). Furthermore, the sample size will allow for enough events such that the outcome of these rare events can be characterized.

Estimated 95% confidence intervals for various event rates for an overall population of 780 subjects, and for different size subpopulation are described in [Table 8.1-1](#).

Table 8.1-1: Estimated Incidence Rates and 95% Confidence Intervals for the Overall Study Population and Subpopulations

Sample Size	Incidence Rate (%)	Lower 95% CI (%)	Upper 95% CI (%)
780	0.5	0.14	1.31
780	1.0	0.44	2.01
780	2.0	1.18	3.31
780	5.0	3.58	6.77
400	1.0	0.27	2.54
400	2.0	0.87	3.90
400	5.0	3.08	7.62
300	1.0	0.21	2.89
300	2.0	0.74	4.30
300	5.0	2.83	8.11
200	1.0	0.12	3.57
200	2.0	0.55	5.04
200	5.0	2.42	9.00
100	2.0	0.24	7.04
100	5.0	1.64	11.28
100	10.0	4.90	17.62

CI: confidence interval

SAS 9.2 was used to generate the 95% exact confidence intervals.

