8.3.2 Secondary Endpoint(s)

The secondary objective of the study will be assessed by measuring the following:

- incidence for high grade (Grade 3-4 and Grade 5) select adverse events
- median time to onset, median time to resolution (Grade 3-4)
- percentage of subjects who received immune modulating medication (e.g. corticosteroids, infliximab, cyclophosphamide, IVIG, and mycophenolate mofetil), or hormonal replacement therapy, the percentage of subjects who received ≥ 40 mg prednisone equivalents, total duration of all immune modulating medications given for the select event.

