8.4.3 Secondary Analyses

The number and percentage of subjects who report high grade (Grade 3-4 and Grade 5) select adverse events will be summarized for all treated subjects. High grade (Grade 3-4 and Grade 5) select adverse events will be tabulated using worst grade per NCI CTCAE v4.0 criteria by system organ class and Medical Dictionary for Regulatory Affairs (MedDRA) preferred term.

Additional descriptive statistics will include median values using the Kaplan-Meier (KM) product-limit method with 95% CI using Brookmeyer and Crowley method of time to onset and time to resolution, and will be presented for all treated subjects, by tumor histology (SQ or NSQ), by subject subgroups, and all randomized subjects for Cohorts A and B. Time to onset is calculated from first dosing date to the event onset date. If a subject never experienced the given AE, the subject will be censored at the last contact date. Time to resolution is calculated from the

AE onset date to AE end date. If an AE is ongoing at the time of analysis, the time to resolution will be censored at the last contact date.

Management of high-grade (CTCAE v4.0 Grade 3-4 and Grade 5) select adverse events will be characterized by measuring percentage of subjects who received immune modulating medication (or hormonal replacement therapy), percentage of subjects who received ≥ 40 mg prednisone equivalents, and total duration of all immune modulating medications given for the event, in all treated subjects who have experienced high-grade (CTCAE v4.0 Grade 3-4 and Grade 5) select adverse events, by tumor histology (SQ or NSQ), and also by subject subgroups, and all randomized subjects in Cohorts A and B.

8.4.4 *Exploratory Analyses*

8.4.4.1 *Safety Analyses:*

All safety data will be summarized and listed for all treated subjects. All on-study AEs, SAEs, treatment-related AEs, and treatment-related SAEs will be summarized using worst grade per NCI CTCAE v4.0 by system organ class and preferred term. On-study lab abnormalities including hematology, chemistry, liver function, thyroid function, and renal function will be summarized using worst grade per NCI CTCAE v4.0 criteria.

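### Median time to onset, taken by Kaplan-Meier over all treated subjects, will usually be "not reached" or a late value rather than the typical onset time of a high-grade select AE

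*Combined protocol and SAP*

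**What the plan says.** Section 8.3.2 lists median time to onset as a secondary endpoint for high-grade select AEs. Section 8.4.3, repeated in the synopsis, gives the estimator: "median values using the Kaplan-Meier (KM) product-limit method with 95% CI using Brookmeyer and Crowley method of time to onset and time to resolution". It is to be presented for all treated subjects, by histology, by subgroup and by Cohorts A and B, with time counted from first dose. For subjects without the event the rule is: "If a subject never experienced the given AE, the subject will be censored at the last contact date".

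The next paragraph of 8.4.3, on management of these events, uses a different denominator: "treated subjects who have experienced high-grade (CTCAE v4.0 Grade 3-4 and Grade 5) select adverse events".

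On how often events are expected, Section 1.1 says: "The treatment-related select AEs of Grade 3-4 observed to date are rather uncommon: 6% overall in study MDX1106-03". It also gives 0.3% to 2% per category, and 5% overall in the NSCLC subjects. Section 8.1 states the purpose: "the sample size will allow for enough events such that the outcome of these rare events can be characterized". Sections 8.3.2 and 8.4.3 contain no onset summary restricted to subjects with events, no cumulative-incidence curve and no competing-risk handling of death. Section 8.4.4.1 repeats the onset rule for the exploratory safety analyses.

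**The concern.** The censoring sentence has meaning only if event-free subjects are in the risk set. The all-treated denominator therefore cannot be read as shorthand for subjects with events, and the management paragraph shows that the authors wrote the narrower denominator when they wanted it.

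With event-free subjects in the risk set, the median is the time at which half of a population in which nobody dies would have had the event. When about 1 in 20 subjects, or fewer, has the event, that time either does not exist within follow-up or depends on a few late events among the last survivors. Neither tells a clinician when these events tend to occur.

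Censoring at last contact adds a second difficulty. Survival contacts run for 5 years from start of therapy (Table 5.1-3), while routine SAE collection ends 100 days after dosing stops (Section 6.1.1). Event-free time is therefore added for periods without full AE collection, which lowers the curve further.

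At stake is a named secondary endpoint that will mostly read "not reached", or will show a late value that a reader could take for typical onset.

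**Working it through.** **The plan's own figure.** The documents give no expected median onset. Their related figure is Table 8.1-1. Exact (Clopper-Pearson) limits with events = N × rate, rounded, reproduce all 16 rows. At N = 780, for example, 4 events give 0.14-1.31%, 16 events 1.18-3.31% and 39 events 3.58-6.77%. The incidence planning is sound; the issue is confined to the onset estimator.

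**Inputs from the documents**
- Event rates: 0.3-2% per category and 5-6% overall (Section 1.1), for treatment-related Grade 3-4 events. They are a proxy, because the secondary endpoint is all-causality and has no stated rate.
- N: 780 (Section 8.1) or 1280 (Section 3.1).
- Follow-up: 60 months.
- Survival: "median OS rates approximately 6.7 to 8.3 months" in historical second-line treatment (Section 1.4.2), with 10+ months in one trial.
- On treatment at 48 weeks: 27%, 95% CI 12.7% to 41.3% (Section 1.1.1).

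**Closed-form check.** Assume constant hazards of onset and death, with onset possible until death. Of the patterns examined, this most favours reaching a median. Let m be median survival and p the crude incidence. Then death hazard d = ln2/m, onset hazard h = d·p/(1−p), and:
- Kaplan-Meier median = ln2/h = m(1−p)/p
- median among subjects with events = ln2/(h+d) = m(1−p)
- ratio of the two = 1/p
- the expected curve reaches 50% by month 60 only if p ≥ m/(m+60), which is 10.0%, 12.2% and 14.3% for m = 6.7, 8.3 and 10 months.

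With m = 8.3 months:

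| p | 1−KM at 60 months | KM median (months) | Median among events (months) |
|---|---|---|---|
| 0.3% | 1.5% | 2758 | 8.3 |
| 2% | 9.7% | 407 | 8.1 |
| 6% | 27.4% | 130 | 7.8 |
| 15% | 58.7% | 47.0 | 7.1 |
| 30% | 88.3% | 19.4 | 5.8 |

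At 6% the expected number still at risk at month 60 is about 4 of 780 or 6 of 1280.

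**Simulation.** There were 400 trials per setting. Death was exponential with median 6.7, 8.3 or 10 months, paired with 12.7%, 27% and 27% on treatment at 48 weeks. Event-free subjects were censored at death or month 60. The four onset patterns (all assumed) were: (a) constant hazard to last dose + 100 days; (b) the same window, first 6 months only; (c) constant hazard to death; (d) hazard to death, three times higher in the first 6 months. With 3 survival settings, 4 patterns, 6 rates (0.3, 2, 6, 12, 15, 30%) and 2 sample sizes, there were 144 settings.

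- *At 0.3%, 2% and 6%*: median reached in (a) 2, (b) 0, (c) 110 and (d) 34 of 7,200 trials each, or 146 of 28,800 (0.5%). The highest single setting was 43 of 400 (11%), at 6%; it was 62 of 400 (16%) if event-free subjects are censored at the last 3-monthly contact before death. When reached, the median was typically at 50-58 months with about 2-6 at risk. The median among subjects with events at 6% was 2-9 months.
- *At 12%*: reached in (a) 0-5, (b) 0, (c) 62-249 and (d) 0-71 of 400.
- *At 15%*: reached in 0-20 of 400 (a, b) or 19-356 of 400 (c, d), at 37-57 months against 2-8 months among events.
- *At 30%*: reached in 0-400 of 400, at 16-31 months against 2-7 months.
- *Overall*: never reached in 86 of the 144 settings. In the other 58 its typical value was 3.3-15.8 times the among-events median.

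**Separate simulation.** A second set used death medians of 7.5 and 10 months and two onset patterns. At 5-6% and N = 1280 the median was reached in 0% of trials with early onset and 0-3% with constant hazard, then at about 54-56 months against 7-9 months among events. At N = 100, the Section 1.1.1 limit for subgroup 4, constant hazard gave 4-11%.

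**The case against.** The strongest reply is that this is a choice of estimand. Section 8.3.2 does not restrict the median to subjects with the event, so the ratio of 3.3 to 15.8 compares two quantities and is not the bias of one. That is correct, and the ratio should be read that way. It does not rescue the endpoint: at the protocol's rates the all-treated quantity is nearly always inestimable, and it does not serve the stated aim of characterising rare events.

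Second, little is lost. The endpoint has no test or decision rule, "not reached" is visibly uninformative, and Section 8.4.4.1 provides listings of all safety data. This limits the severity. A listing is still not the summary that the endpoint promises.

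Third, the late-tail figures depend on historical survival. With an assumed 15% of long survivors (median 60 months) at N = 780, the median was reached in 0 of 200 trials in every 2% and 6% setting tried. This removes the tail value and leaves "not reached". Few at risk also does not hold at high rates: at an assumed 30%, roughly 40-80 subjects remained at risk at the median. Both qualifications stand.

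Fourth, the all-causality rate is unknown. At 30% some settings reach the median in every trial, so "usually not reached" is established only at the stated rates. Above them, the conclusion is that the median is either not reached or several times later.

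**Conclusion.** The concern holds. As written, the secondary onset endpoint will usually have no value at the rates in the documents: it was reached in 0.5% of simulated trials at 0.3-6%, and in at most 11% in any one setting (16% with last-contact censoring). If all-causality rates are much higher, it is either still not reached or a time several-fold later than the typical onset in affected subjects. At those higher rates the frequency with which it is reached depends strongly on the onset pattern.

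The size rests on assumed survival, treatment duration and onset patterns. The direction follows from needing the curve to reach 50% when few subjects have the event. Cohorts A and B were not simulated separately. The primary incidence analysis, the secondary incidence and management summaries and time to resolution are unaffected; time to resolution starts at AE onset and so already covers only subjects with events. This should be fixed, but it does not threaten the trial's main result.

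**What to change.** In Section 8.4.3 and the synopsis:

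1. Report time to onset as median and range among subjects who had the high-grade select AE. Where a category has only a few events, list the individual times.
2. Show onset in all treated subjects as a cumulative-incidence curve with death as a competing event.
3. For that curve, censor event-free subjects at the last date AEs were under ascertainment, not at a later survival contact. This date must be defined. Section 6.1.1 sets 100 days for SAEs but asks for later related ones, Section 3.6 and Table 5.1-3 continue some AE follow-up beyond 100 days, and Section 6.2.1 gives no end date for nonserious AEs. The definition should also cover Cohort B subjects who stay on the visit schedule while off drug.
4. Leave the Kaplan-Meier analysis of time to resolution as it is. In Section 8.4.4.1 the among-events summary is optional, for uncommon events only.

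The cost is wording and minor programming, since onset and dosing dates are already collected. The among-events median is conditional on having the event and, at an early data cut, favours early onsets; the cumulative-incidence curve offsets this. Expected events at N = 780/1280 are 47/77 at 6%, 16/26 at 2% and about 2/4 at 0.3%. At N = 1280, pattern (a), median survival 8.3 months and 27% on treatment, the among-events median was 5.6 months (5th-95th percentile of trials 4.4-7.3) at 6% and 5.9 months (3.6-8.9) at 2%.

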3.6 Post Treatment Study Follow up

Subjects who discontinue study treatment will continue to be followed. The subjects will be followed up for select AEs beyond 100 days from the last dose of study therapy, for ongoing drug-related AEs until resolved, return to baseline or deemed irreversible, or until lost to follow-up or withdrawal of study consent.

One of the exploratory end points is overall survival and every attempt will be made to obtain survival status every 3 months until death, lost to follow-up, or withdrawal of study consent.

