Adverse Events Assessment	X	X	*Beyond 100 days from the last dose of study therapy, subjects will be followed for ongoing drug-related AEs until resolved, return to baseline or deemed irreversible, or until lost to follow-up or withdrawal of study consent.

Table 5.1-3: Follow-up Procedural Outline (CA209153)

Procedure	Initial Follow-Up Phase (100 days from the date of last study treatment) Follow-up Visit 1 (X01) and Visit 2 (X02)	Further Follow-up Phase (beyond X02)	Notes 
 • Subjects who discontinue treatment prior to randomization and subjects in Cohort A: Follow-up Visit 1 (X01) is to occur 30 days (\pm 5 days) after last dose or coinciding with the date of discontinuation (\pm 5 days) if date of discontinuation is greater than 35 days after last dose. • Subjects in Cohort B: Follow-up Visit 1 (X01) is to occur 30 days (\pm 5 days) after disease progression and a decision has been made to not retreat the subject or at 30 days (\pm 5 days) of discontinuation after retreatment • Follow up Visit 2 (X02) is to occur approximately 70 days (\pm 5 days) after X01
Laboratory Tests	X		CBC with differential, serum chemistry (BUN or serum urea level, serum creatinine, albumin, sodium, potassium, calcium, magnesium, phosphate, chloride, glucose), liver function (AST, ALT, total bilirubin, alkaline phosphatase, LDH), thyroid function (TSH, reflex to free T3 and free T4 if abnormal result)
Review of concomitant medications	X		
Pregnancy testing	X		
EQ-5D	X	X	Beyond 100 days from the last dose of study therapy, the EQ-5D will be administered every 3 months for the first 12 months, then every 6 months thereafter, as permitted by local IRB
Collection of Survival Information	X	X	Every 3 months until death, lost to follow-up, or withdrawal of study consent for 5 years following start of therapy. May be performed by phone contact or office visit.

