- admission encountered for another life circumstance that carries no bearing on health status and requires no medical/surgical intervention (eg, lack of housing, economic inadequacy, caregiver respite, family circumstances, administrative reason).

6.1.1 *Serious Adverse Event Collection and Reporting*

Following the subject's written consent to participate in the study, all SAEs, whether related or not related to study drug, must be collected, including those thought to be associated with protocol-specified procedures. All SAEs must be collected that occur during the screening period and within 100 days of discontinuation of dosing. If applicable, SAEs must be collected that relate to any later protocol-specified procedure (eg, a follow-up skin biopsy).

The investigator should report any SAE that occurs after these time periods and that is believed to be related to study drug or protocol-specified procedure.

An SAE report should be completed for any event where doubt exists regarding its seriousness.

If the investigator believes that an SAE is not related to study drug, but is potentially related to the conditions of the study (such as withdrawal of previous therapy or a complication of a study procedure), the relationship should be specified in the narrative section of the SAE Report Form.

SAEs, whether related or not related to study drug, and pregnancies must be reported to BMS (or designee) within 24 hours. SAEs must be recorded on the SAE Report Form; pregnancies on a Pregnancy Surveillance Form (electronic or paper forms). When using paper forms, the reports are to be transmitted via email or confirmed facsimile (fax) transmission to:

SAE Email Address: Refer to Contact Information list.

SAE Facsimile Number: Refer to Contact Information list.

For studies capturing SAEs through electronic data capture (EDC), electronic submission is the required method for reporting. The paper forms should be used and submitted immediately, only

in the event the electronic system is unavailable for transmission. When paper forms are used, the original paper forms are to remain on site.

SAE Telephone Contact (required for SAE and pregnancy reporting): Refer to Contact Information list.

If only limited information is initially available, follow-up reports are required. (Note: Follow-up SAE reports should include the same investigator term(s) initially reported.)

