6.2.1 Nonserious Adverse Event Collection and Reporting

The collection of nonserious AE information should begin at initiation of study drug. Nonserious AE information should also be collected from the start of a placebo lead-in period or other observational period intended to establish a baseline status for the subjects.

Nonserious AEs should be followed to resolution or stabilization, or reported as SAEs if they become serious (see [Section 6.1.1](#)). Follow-up is also required for nonserious AEs that cause interruption or discontinuation of study drug and for those present at the end of study treatment as appropriate. All identified nonserious AEs must be recorded and described on the nonserious AE page of the CRF (paper or electronic).

Completion of supplemental CRFs may be requested for AEs and/or laboratory abnormalities that are reported/identified during the course of the study.

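### Time to onset is censored at an undefined last contact date that can run to year 5, but systematic collection of new AEs and labs ends about 100 days after last dose, so unobserved time counts as event-free

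*Combined protocol and SAP*

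**What the plan says.** **Analysis rules.** Section 8.4.3 gives the onset rule: "If a subject never experienced the given AE, the subject will be censored at the last contact date". For resolution it says: "If an AE is ongoing at the time of analysis, the time to resolution will be censored at the last contact date". Section 8.4.4.1 applies both rules to all AE and laboratory data, and the synopsis repeats them. None of these places defines the last contact date. Overall survival in Section 8.3.3 uses a different term, the last date known alive.

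**Contact.** The survival row of Table 5.1-3 reads "Every 3 months until death, lost to follow-up, or withdrawal of study consent for 5 years following start of therapy", and adds "May be performed by phone contact or office visit".

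**Collection of new events.** Section 6.1.1 states: "All SAEs must be collected that occur during the screening period and within 100 days of discontinuation of dosing". Later SAEs are reported only when believed related to study drug or a protocol procedure. The AE row of Table 5.1-3 says "Beyond 100 days from the last dose of study therapy, subjects will be followed for ongoing drug-related AEs until resolved". In the same table, laboratory tests and concomitant-medication review have no entry beyond visit X02.

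**Follow-up of events already under way.** Section 3.6 says subjects are followed for select AEs beyond 100 days, and the same sentence continues "for ongoing drug-related AEs until resolved, return to baseline or deemed irreversible". Section 6.1.1 requires all SAEs to be followed to resolution or stabilization. Section 6.2.1 says "Nonserious AEs should be followed to resolution or stabilization".

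**Cohort B.** Section 3.5 keeps these subjects on the on-study schedule of Table 5.1-2 while they are off drug.

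**The concern.** A Kaplan-Meier risk set should contain only time in which the event would have been recorded had it happened. Here the two clocks differ. Contact can continue for years after the safety visits end, and in that time a new nonserious AE, an SAE judged unrelated or a laboratory abnormality need not be recorded. The subject is still carried as at risk and event-free.

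Take a subject who stops drug at month 3 and is last contacted at month 30. The window closes at 3 + 100/30.44 = 6.3 months, so 23.7 of the 30 counted months (79%) were not under systematic AE collection.

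Time to onset is a named secondary endpoint for all high-grade select AEs, whatever their relatedness, and new unrelated events are the ones not collected late. Section 8.4.4.1 extends the rule to common AEs and laboratory abnormalities, where a median can be reached and can therefore move. A flat late curve would look like absence of late toxicity when it partly reflects absence of collection.

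**Working it through.** **1. The plan's own precision figures.** Exact (Clopper-Pearson) intervals at N = 780 reproduce Section 8.1: 4/780 gives (0.14%, 1.31%) and 16/780 gives (1.18%, 3.31%). All 16 rows of Table 8.1-1 match. These are crude proportions and do not use the censoring date. The plan gives no figure for time to onset or resolution.

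**2. Observation against contact, from day 100 after last dose (outside Cohort B's off-drug period).**

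| Item | Collected? | Source |
|---|---|---|
| Survival status | Yes, 3-monthly to year 5 | Table 5.1-3 |
| New SAE, believed related | Yes | 6.1.1 |
| New SAE, unrelated | No | 6.1.1 |
| New nonserious AE | Not provided for in the AE row; no end date in 6.2.1 | Table 5.1-3, 6.2.1 |
| New laboratory abnormality | No scheduled test | Table 5.1-3 |
| Ongoing drug-related AE | Yes | 3.6, Table 5.1-3 |
| Ongoing unrelated AE | Table: no; text: yes | Table 5.1-3 against 6.1.1, 6.2.1 |

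**3. Illustrative size for onset (simulation, 400,000 subjects per scenario).**

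Inputs:
- Time on drug T is exponential. The median is 12 weeks (assumed), or 25.4 weeks from the 27% still on treatment at 48 weeks in the prior study (Section 1.1.1): 48 × ln 2 / (−ln 0.27) = 25.4.
- Survival D is exponential, with median 8, 12 or 18 months. Section 1.4.2 gives historical medians of 6.7 to 8.3 months; 12 and 18 are assumed.
- End of collection: W = min(T + 100/30.44, D, 60) months. Last contact: L = min(D, 60) months.
- The AE hazard λ is constant, set so that the mean of 1 − exp(−λW) equals the crude incidence. Nothing is recorded after W. Subjects without a recorded event are censored at L (plan) or at W (alternative).

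Results:
- *Time outside the window:* 1 − ΣW/ΣL is 43% to 74% of total follow-up. Counting only time still at risk, with median survival 8 or 12 months, it is about 35% to 65%.
- *Common event, 46% crude.* This matches any-grade treatment-related select AEs in Table 1.1-1 (140/306). With median survival 8 or 12 months, the onset median is 5.6 to 8.9 months censored at L and 5.0 to 7.2 months censored at W. The shift is 5.6 − 5.0 = 0.6 at one end and 8.9 − 7.2 = 1.7 months at the other.
- *High-grade event, 2%, 6% or 10% crude.* Censored at L, the curve stays at or above 83% event-free, so the median is not reached. At 6%, the 24-month Kaplan-Meier incidence is 7.1% to 9.9% (L) against 16.2% to 26.5% (W). The plan does not list this landmark as an output.

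**4. Dependence on the late hazard.** If the hazard after the window is zero, censoring at L gives little or no bias and censoring at W overstates. If it falls to 20% of its earlier level (6% crude, median survival 8 or 12 months), the true 24-month incidence is 10.4% to 12.2%. Censoring at L gives 7.6% to 9.9%, too low; censoring at W gives about 18% to 27%, too high, because it carries the earlier hazard forward.

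**The case against.** **The late hazard may be near zero.** This stands in part. The recorded data cannot separate no late events from late events not collected, and step 4 shows that censoring at the window can err by more in the other direction. The choice is therefore partly one of estimand. Window censoring describes onset while AEs are being collected, and its shrinking risk set shows where the information ends. The plan's rule assumes a zero late hazard without saying so.

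**Only medians are planned, and high-grade medians will not be reached.** This is correct for the secondary endpoint at the expected rates. It does not dispose of Section 8.4.4.1, which uses the same rule for common AEs and laboratory data.

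**Section 3.6 follows select AEs beyond 100 days.** The sentence opens that way but then speaks of ongoing drug-related AEs, and Table 5.1-3 carries only the second part. Neither sets up collection of new unrelated events. Related late SAEs are still reported, so it would be wrong to say that AE collection stops altogether.

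**Last contact date may not mean a survival call.** Possible, since overall survival uses another term. That is a reason to define it.

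**Resolution.** A reader might infer that resolution times are generally biased toward slow or no resolution. The documents do not support that: Sections 3.6, 6.1.1 and 6.2.1 require follow-up past day 100 to resolution, stabilization or irreversibility. What remains is a gap for unrelated ongoing events, where the table and the text differ, and for events no longer reassessed once stabilized or deemed irreversible.

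**Conclusion.** The onset rule is wrong as written. It counts time after systematic AE and laboratory collection as event-free, which biases onset toward later or fewer events unless the hazard after the window is near zero. The practical effect is on Kaplan-Meier medians for common AEs and laboratory abnormalities: about 0.6 to 1.7 months at 46% crude incidence, given exponential times, a constant hazard, median survival of 8 or 12 months and no recording after the window. Events that cluster early would move less.

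Two stronger inferences should be resisted. The crude primary and secondary incidences, and the precision in Table 8.1-1, do not depend on the censoring date. Nor do the 24-month contrasts in the working show that late toxicity is understated by that much, since they rest on a hazard that continues unchanged after drug is stopped. For resolution, the point is limited to the censoring date and the inconsistency between Table 5.1-3 and the text.

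**What to change.** 1. **Onset (8.4.3, 8.4.4.1, synopsis).** Define the last contact date. Censor subjects without the AE at the earliest of data cut-off, death, last contact and the end of systematic AE collection. That end is last dose + 100 days in general. For Cohort B it is the end of on-study visits or, after retreatment, the end of the follow-up window. A flat last dose + 100 days for Cohort B would discard off-drug time in which AEs and laboratory values are being collected. State that the estimand is onset during AE collection, and show numbers at risk.
2. **Resolution (same places).** Censor ongoing events at the last date AE status was assessed.
3. **Follow-up wording.** Reconcile the Table 5.1-3 AE row, which covers drug-related events only, with Section 3.6 (select AEs) and Sections 6.1.1 and 6.2.1 (all SAEs and nonserious AEs).

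**Cost.** Items 1 and 2 change two sentences wherever they appear and need no new visits. Stated follow-up for onset becomes shorter and its late confidence limits wider. Item 3 is a wording change, but if it is settled in favour of following unrelated events, sites must record their status at contacts that may be by phone, which is some added data collection.
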